9.2.3. Combination F

Phase 1b: Before expanding cohorts F1, F2, and F3 into the Phase 2 cohort expansion, the safety of the combination in that cohort must be confirmed in DLT-evaluable patients in the Phase 1b lead-in.

Up to 12 patients will be randomized into each cohort in the Phase 1b lead-in and evaluated for DLT during the first treatment cycle (4 weeks) as follows:

- If ≤ 1 of 6 patients experience DLT, the cohort will be expanded to enroll up to 14 additional patients in the Phase 2 cohort expansion.
- If 2 of 6 patients experience DLT, the cohort will be expanded to enroll up to 6 additional DLT-evaluable patients in the Phase 1b lead-in part of the study:
 - If ≤ 3 of 12 patients experience DLT, the cohort will be expanded to enroll up to 8 additional patients in the Phase 2 cohort expansion;
 - If ≥ 4 of up to 12 patients experience DLT, enrollment in the specific cohort will be discontinued.
- If ≥ 3 of up to 6 patients experience DLT, enrollment in the specific cohort will be discontinued.

Table 29 shows the probability of expanding enrollment of a cohort into Phase 2 based on the DLT rates observed for 6 or 12 DLT-evaluable patients in Phase 1b and a range of underlying true DLT rates. For example, for a DLT that occurs in 10% of patients, there is a 97% probability of confirming safety and expanding the corresponding cohort.

Table 29. Combination F: Probability of Expanding Dose Level

True underlying DLT rate	10%	20%	30%	40%	50%	60%	70%	80%	90%
Probability of expanding dose level	0.97	0.82	0.56	0.31	0.14	0.05	0.01	0.002	<0.0001

DLT = dose limiting toxicity.

9.3. Sample Size Determination

9.3.1. Combination A

The number of patients to be enrolled in Combination A may depend upon the observed safety profile, which will determine the number of patients at each dose level and the number of dose levels explored. The total number of patients treated in Combination A (Phase 1b and Phase 2 combined) is expected to be approximately 253.

9.3.1.1. Sample Size Determination for Utomilumab and Avelumab for NSCLC Cohorts A1, A2, and A3

There will be up to 3 dose level cohorts of patients with NSCLC that will be assessed for efficacy independently. The null hypothesis that the objective response rate does not exceed 15% ($H_0: ORR \leq 15\%$) will be tested against the alternative ($H_1: ORR > 15\%$) for each cohort using the binomial distribution at one-sided level of significance $\alpha=0.05$. For each cohort, data from the Phase 1b lead-in and Phase 2 will be combined for this assessment.

Within each cohort, 28 patients will provide at least 80% power to reject the null hypothesis if the true ORR is at least 35% ($ORR \geq 35\%$).

At the end of the study, if there are ≤ 7 objective responders of 28 patients treated in a given cohort (6 +22 patients), then it will be declared that for that cohort, the null hypothesis cannot be rejected, or that clinically meaningful activity has not been demonstrated. If there are ≥ 8 objective responders of 28 patients treated in a given cohort, the null hypothesis will be rejected for that cohort and clinically meaningful activity has been demonstrated.

9.3.1.2. Sample Size Determination for Utomilumab and Avelumab for Melanoma Cohort A4

The primary objective for Cohort A4 is to test null hypothesis that the ORR in melanoma patients treated with combination of utomilumab and avelumab does not exceed 15% ($H_0: ORR \leq 15\%$). The null hypothesis will be tested against the alternative ($H_1: ORR > 15\%$) at one-sided level of significance $\alpha=0.05$ using the binomial distribution.

Twenty-eight patients will provide at least 80% power to reject the null hypothesis if the true ORR is at least 35% ($ORR \geq 35\%$).

At the end of the study, if there are ≤ 7 objective responders of 28 patients in this cohort, then it will be declared that the null hypothesis cannot be rejected, or that clinically meaningful activity has not been demonstrated. If there are ≥ 8 objective responders of 28 patients treated in the cohort, the null hypothesis will be rejected and clinically meaningful activity has been demonstrated.

9.3.1.3. Sample Size Determination for Utomilumab and Avelumab for SCCHN Cohort A5

The primary objective for Cohort A5 is to test null hypothesis that the ORR in SCCHN patients treated with combination of utomilumab and avelumab does not exceed 20% ($H_0: ORR \leq 20\%$). The null hypothesis will be tested against the alternative ($H_1: ORR > 20\%$) at one-sided level of significance $\alpha=0.05$ using the binomial distribution.

Thirty-five patients will provide at least 80% power to reject the null hypothesis if the true objective response rate is at least 40% ($ORR \geq 40\%$).

At the end of the study, if there are ≤ 11 objective responders of 35 patients in this cohort, then it will be declared that the null hypothesis cannot be rejected, or that clinically meaningful activity has not been demonstrated. If there are ≥ 12 objective responders of 35 patients treated in the cohort, the null hypothesis will be rejected and clinically meaningful activity has been demonstrated.

9.3.1.4. Sample Size Determination for Utomilumab and Avelumab for TNBC Cohort A6, SCLC Cohort A7, and First-Line NSCLC Cohorts A8, A9 and A10

Based on the emerging data, PD-L1 expression status shows prognostic significance for NSCLC patients. Thus, inclusion criteria for Cohort A8 are updated to add the requirement of having positive PD-L1 expression status. To reflect this change, at least 20 PD-L1 positive patients will be enrolled in the Cohort A8. Overall sample size for Cohort A8 may be larger (N= up to 26, based primarily on internal data that 6 patients [$\sim 30\%$] will need replacement) and can include PD-L1 negative patients that were enrolled prior to Protocol Amendment #6.

Twenty (20) patients each will be enrolled in Cohorts A6, A7, A9 and A10.

With 20 patients in each of the TNBC, SCLC cohorts, and 20 PD-L1 positive patients in first-line (1L) NSCLC cohorts, ORR can be estimated with a maximum standard error of 11.2%. Table 30. provides the exact binomial 90% confidence intervals for ORR based on different observed responses in a cohort.

Table 30. Sample Size and Exact 90% CI for ORR in Combination A, Cohort A6-A10.

N per cohort	Number of responses	Observed ORR	90% CI for ORR
20	1	5%	(0.3% - 21.6%)
	2	10%	(1.8% - 28.3%)
	3	15%	(4.2% - 34.4%)
	4	20%	(7.1% - 40.1%)
	5	25%	(10.4% - 45.6%)
	6	30%	(14.0% - 50.8%)
	7	35%	(17.7% - 55.8%)
	8	40%	(21.7% - 60.6%)
	9	45%	(25.9% - 65.3%)
	10	50%	(30.2% - 69.8%)
	11	55%	(34.7% - 74.1%)
	12	60%	(39.4% - 78.3%)
	13	65%	(44.2% - 82.3%)
	14	70%	(49.2% - 86.0%)
	15	75%	(54.4% - 89.6%)

9.3.2. Combination B: Sample Size Determination for PF-04518600 and Avelumab

Up to 105 patients (Phase 1b and Phase 2 combined) may be enrolled for Combination B treatment.

For Phase 1b of Combination B, due to the dynamic nature of the Bayesian allocation procedure, the exact sample size of the “Up-and-Down” matrix design using the mTPI approach cannot be determined in advance. It is expected that up to 30 patients will need to be enrolled in Phase 1b using the mTPI approach.

For Phase 2 of this combination, 25 patients will be enrolled from each of 3 tumor types: NSCLC, melanoma, and SCCHN. Thus up to 75 patients will be enrolled in Phase 2 for Combination B.

With 25 patients, ORR can be estimated with a maximum standard error of 10%.

Table 31 provides the exact binomial 90% confidence intervals for ORR based on different observed responses in a cohort.

Table 31 Sample Size and Exact 90% CI for ORR in Combinations B, C, and D

N per cohort	Number of responses	Observed ORR	90% CI for ORR
25	1	4%	(0.2% - 17.6%)
	2	8%	(1.4% - 23.1%)
	3	12%	(3.4% - 28.2%)
	4	16%	(5.7% - 33.0%)
	5	20%	(8.2% - 37.5%)
	6	24%	(11.0% - 42.0%)
	7	28%	(13.9% - 46.2%)
	8	32%	(17.0% - 50.4%)
	9	36%	(20.2% - 54.4%)
	10	40%	(23.6% - 58.3%)
	11	44%	(27.0% - 62.1%)
	12	48%	(30.5% - 65.9%)
	13	52%	(34.1% - 69.5%)
	14	56%	(37.9% - 73.0%)
	15	60%	(41.7% - 76.4%)
	20	80%	(62.5% - 91.8%)

9.3.3. Combination C: Sample Size Determination for PD 0360324 and Avelumab

Up to 80 patients (Phase 1b and Phase 2 combined) may be enrolled for Combination C treatment. For the Phase 1b part of Combination C, due to the dynamic nature of the Bayesian allocation procedure, the exact sample size of the “Up-and-Down” matrix design using the mTPI approach cannot be determined in advance. It is expected that up to 30 patients will need to be enrolled in the Phase 1b part using the mTPI approach and backfill.

For the Phase 2 part of this combination, 2 tumor-specific cohorts of 25 patients each with the selected tumor types chosen for evaluation will be enrolled. The selected tumor types will be selected following completion of Phase 1b for the combination.

With 25 patients in each cohort, ORR can be estimated with a maximum standard error of 10%. [Table 31](#) provides the exact binomial 90% confidence intervals for ORR based on different observed responses in a cohort.

9.3.4. Combination D: Sample Size Determination for Utomilumab and PF-04518600 and Avelumab

Up to 122 patients (Phase 1b and Phase 2 combined) may be enrolled for Combination D treatment.

For the Phase 1b part of Combination D, due to the dynamic nature of the Bayesian allocation procedure, the exact sample size of the “Up-and-Down” matrix design using the mTPI approach cannot be determined in advance. It is expected up to 72 patients may be enrolled in the Phase 1b part using the mTPI approach and backfill.

For the Phase 2 part of this combination, 2 tumor-specific cohorts of 25 patients each with the selected tumor types chosen for evaluation may be enrolled. The selected tumor types will be selected following completion of Phase 1b for the combination.

The level of clinical activity observed in the Phase 1b part of Combination D, did not support further development. Therefore, Phase 2 is not planned.

With 25 patients in each cohort, ORR can be estimated with a maximum standard error of 10% within each tumor-specific cohort. [Table 31](#) provides the exact binomial 90% confidence intervals for ORR based on different observed responses in a cohort.

9.3.5. Combination F: Sample Size Determination for CMP-001 and Avelumab and Utomilumab or PF-04518600

Up to 20 patients will be randomized in each of the Cohorts F1, F2 and F3 at the selected dose level.

With 20 patients in each cohort, ORR can be estimated with a maximum standard error of 0.112. The exact binomial 90% CIs for ORR based on different observed responses for each of the cohorts F1, F2 and F3 are as presented in [Table 32](#).

Table 32 Sample Size and Exact 90% Confidence Intervals for Objective Response Rate in Combination F (Cohorts F1 to F3)

Number per cohort	Number of responses	Observed ORR	90% CI for ORR
20	1	5%	(0.3% - 21.6%)
	2	10%	(1.8% - 28.3%)
	3	15%	(4.2% - 34.4%)
	4	20%	(7.1% - 40.1%)
	5	25%	(10.4% - 45.6%)
	6	30%	(14.0% - 50.8%)
	7	35%	(17.7% - 55.8%)
	8	40%	(21.7% - 60.6%)
	9	45%	(25.9% - 65.3%)
	10	50%	(30.2% - 69.8%)
	11	55%	(34.7% - 74.1%)
	12	60%	(39.4% - 78.3%)
	13	65%	(44.2% - 82.3%)
	14	70%	(49.2% - 86.0%)
	15	75%	(54.4% - 89.6%)

CI=confidence interval; ORR=objective response rate.

9.4. Efficacy Analysis

All efficacy analyses will be performed for each cohort and combination separately including Phase 1b lead-in and Phase 2 patients in the full analysis set.

In the definitions below, start date refers to the date of randomization for the NSCLC cohorts in Combination A, for all the cohorts in Combination F, and to the date of first dose of study treatment for all other cohorts in the other Combinations. For Cohort A8, A9 and A10, analysis will be performed for PD-L1 positive patients as assessed by central lab.

OR is defined as a CR or PR per RECIST v1.1 from the start date until disease progression or death due to any cause. Both CR and PR must be confirmed by repeat assessments performed no less than 4 weeks after the criteria for response are first met. Objective response rate (ORR) is defined as the proportion of patients with a confirmed CR or PR per Investigator's assessment according to RECIST v.1.1. Confirmed responses are those that persist on repeat tumor assessments for at least 4 weeks after initial documentation of response. Otherwise, the patient will be counted as a non-responder in the assessment of ORR. Additionally, patients with inadequate data for tumor assessment (eg, no baseline assessment or no follow up assessments) will be considered as non-responders in the assessment of ORR. The two-sided exact 90% CIs for ORR will be calculated.

Progression-Free Survival (PFS) is defined as the time from the start date to the date of disease progression by RECIST v1.1 or death due to any cause, whichever occurs first. PFS data will be censored on the date of the last adequate tumor assessment for patients who do not have an event (PD or death), for patients who start new anti-cancer treatment prior to an event, or for patients with an event after 2 or more missing tumor assessments. Patients who do not have a baseline tumor assessment or who do not have any post-baseline tumor

assessments will be censored on the start date unless death occurred on or before the time of the second planned tumor assessment in which case the death will be considered an event.

Time to Tumor Response (TTR) is defined for patients with confirmed objective response (CR or PR) as the time from the start date to the first documentation of objective tumor response.

Duration of Response (DR) is defined for patients with confirmed objective response (CR or PR) as the time from the first documentation of objective tumor response to the first documentation of objective tumor progression or to death due to any cause, whichever occurs first.

Overall Survival (OS) is defined as the time from the start date to the date of death. Patients without an event (death) will be censored at the date of last contact.

TTR will be summarized using simple descriptive statistics (eg median and range). DR, PFS, and OS will be analyzed using Kaplan-Meier methods and descriptive statistics. Point estimates will be presented with their 90% and 95% confidence intervals. In addition, progression date, death date, date of first response, and last tumor assessment date will be listed, together with best overall response (BOR), TTR, DR, and PFS.

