b. From C2D1, if IT is not feasible then CMP-001 should be administered in peritumoral region. If peritumoral administration is not feasible, then SC administration in an area of the draining lymph node where primary disease exists should be implemented. If any of the above is not feasible, then SC (either arm, thigh or anterior abdominal wall) should be implemented.

Detailed instructions for CMP-001 administration, including tumor lesion selection and dose splitting, are provided in [Appendix 4](#) and in the Injection Manual.

Statistical Analyses

DLT is the primary endpoint for Phase 1b lead-in. The DLT-evaluable data set includes all enrolled patients in Phase 1b who are eligible for the study, receive at least 1 dose of study treatment, and either experience DLT or complete the DLT observation period. For Combinations A, B, C, and D, the DLT observation period is the first 2 cycles (8 weeks) of treatment. For Combination F, the DLT observation period will be 4 weeks including the first two weekly SC injections and the subsequent two weekly IT administrations.

Patients without DLTs who withdraw from study treatment before receiving at least 75% of the prescribed doses for all investigational products in the combination for reasons other than treatment-related toxicity (eg, missed appointments or development of rapidly progressing disease) are not evaluable for DLT.

Analyses of DLT are based on the DLT-evaluable set. The occurrence of DLTs and AEs constituting DLTs will be summarized and listed per cohort for patients in the Phase 1b lead-in (Combination A and Combination F) and summarized and listed for all patients in the Phase 1b lead-in (Combinations B, C, and D).

OR is the primary endpoint for Phase 2. OR is defined as CR or PR per RECIST v1.1 from the randomization in the study (randomized cohorts) or first dose (non-randomized cohorts) until disease progression or death due to any cause. Both CR and PR must be confirmed by repeat assessments performed no less than 4 weeks after the criteria for response are first met. Objective response rate (ORR) is defined as the proportion of patients with a confirmed CR or PR per Investigator's assessment according to RECIST v.1.1. The two-sided exact 90% CIs for ORR will be calculated.

SCHEDULE OF ACTIVITIES

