23. **Tumor Assessments:** The decision for body areas to be scanned will depend on the disease under study and extent of disease. Imaging may include chest, abdomen and pelvis CT or MRI scans; brain CT or MRI scan, and bone scans (or CT/¹⁸F-FDG-PET/MRI for bone imaging). The CT scans should be performed with contrast agents unless contraindicated for medical reasons. The minimum recommended body areas to be scanned depending on malignancy are detailed in the Imaging Manual. Baseline tumor assessment must be performed within 28 days prior to randomization. The same imaging technique used to characterize each identified and reported lesion at baseline will be employed in the following tumor assessments. Antitumor activity will be assessed through radiological tumor assessments conducted at screening and every 8 weeks until disease progression regardless of initiation of subsequent anticancer therapy. The allowable time window for disease assessments is ±7 days while on treatment and whenever disease progression is suspected (eg, symptomatic deterioration). In case partial response (PR), complete response (CR), or Progressive Disease (PD) is observed according to RECIST v.1.1, tumor assessments should be repeated at least 4 weeks after initial documentation. Tumor assessments should be repeated at End of Treatment/Withdrawal if not done in the previous 4 weeks and prior response is other than confirmed PD. Timing should follow calendar days and should not be adjusted for delays in cycle starts. After 1 year from randomization, tumor assessments will be conducted less frequently, ie, at 12-week (after 1 year) and 16-week (after 2 years) intervals, respectively. Bone scans (or CT/¹⁸F-FDG-PET/MRI) are required at baseline only if bone metastases are known or suspected outside the body areas scanned (CT/MRI), then every 16 weeks only if bone metastases are present at baseline. Otherwise bone imaging is required only if new bone metastasis are suspected and at the time of confirmation of complete response for patients who have bone metastases. Assessment of response will be made using RECIST version 1.1 (see [Section 7.6, Appendix 1](#)).

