5.6. Concomitant Medications

Medications or vaccinations specifically prohibited in the exclusion criteria are also not allowed during the active treatment period, except for administration of the inactivated influenza vaccine. Because multiple novel combinations will be explored during this study, live vaccines are not allowed during the active treatment period and for 90 days after the last dose of study treatment.

If there is a clinical indication for one of these or other medications or vaccinations specifically prohibited during the trial, discontinuation from study therapy or medication/vaccination may be required. The final decision on any supportive therapy or vaccination rests with the Investigator and/or the patient's primary physician. However, the decision to continue the patient on study therapy or medication/vaccination schedule requires the mutual agreement of the Investigator, the Sponsor, and the patient.

Concomitant treatment considered necessary for the patient's wellbeing may be given at discretion of the treating physician.

Concomitant medications and treatments, including herbal supplements, will be recorded from 28 days prior to the start of study treatments and up to 90 days after the last dose of study treatment. All concomitant medications should be recorded in the CRF including supportive care drugs (eg, antiemetic treatment and prophylaxis), and the drugs used to treat adverse events or chronic diseases, and non-drug supportive interventions (eg, transfusions). Concomitant treatments will not be collected for patients who initiate subsequent anticancer therapy.

Concurrent anticancer therapy with agents other than study treatments is not allowed. Medications intended solely for supportive care (eg, antiemetics, analgesics, megestrol acetate for anorexia) are allowed.

Recommended medications to treat infusion-related reactions, hypersensitivity reactions and flu-like symptoms, tumor lysis syndrome and immune-related events are reported in [Section 5.3.7.3.1](#), [Section 5.3.7.3.2](#), [Section 5.3.7.3.3](#), and [Section 5.3.7.3.4](#), respectively.

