- Prophylactic use: prophylactic use, eg, for the prevention of acute infusion-related reactions, constitutes concomitant use and is prohibited except stress steroids to prevent severe CRS reactions in patients enrolled into Combination F as specified in [Section 5.3.5.2](#).
- Intranasal, inhaled, topical steroids, or local steroid injections (eg, intra-articular injection) are permitted.
- There are no prohibited therapies during the Post-Treatment Follow-up Phase.

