6.3. Follow-up

For follow-up procedures see the [Schedule of Activities](#) and Assessments section ([Section 7](#)).

Patients should be evaluated up to 90 days (30 days, 60 days, and 90 days) after last dose of investigational product(s) for safety. Patients continuing to experience toxicity following discontinuation of investigational products will continue to be followed at least every 4 weeks regardless of initiation of new anticancer treatment until resolution or determination, in the clinical judgment of the Investigator, that no further improvement is expected. Follow-up beyond 30 days after last dose of investigational products product(s) may be performed either via a clinic visit or by remote contact (eg, telephone), with subsequent clinic visits requested if any concerns are noted during the telephone call.

Physical examination, ECOG status, vital signs, and safety laboratory measurements are not required for patients who initiate new anticancer treatment, unless the patient continues to experience toxicity following discontinuation of the investigational products. Contraception check and serum/urine pregnancy tests are required for all patients who enter Follow-up regardless of initiation of subsequent anticancer therapy. Patients whose disease has not progressed at the time of treatment discontinuation will enter into disease follow-up (for tumor assessment).

Patients will be followed for survival, independently of time of disease progression or initiation of subsequent anticancer therapy, for at least 2 years after randomization of the last patient in the randomized cohorts and for at least 2 years after first dose of the last patient for the non-randomized cohorts unless lost to follow-up, consent withdrawal, or study discontinued by the Sponsor. Patients will be contacted every 3 months for survival status and subsequent anticancer treatment.

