The best overall response is the best response recorded from the start of the treatment/randomization until disease progression/recurrence (taking as reference for PD the smallest sum on study). For CR and PR, the patient's best response assignment will depend on the achievement of both measurement and confirmation criteria. CR and PR must be confirmed by 2 measurements at least 4 weeks apart. In the case of SD, follow up measurements must have met the SD criteria at least once after start of the treatment/randomization at a minimum interval of 6 weeks.

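### The Phase 2 response window does not close at the start of new anticancer therapy, so a confirmed response on another drug would count for the study combination

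*Protocol*

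**What the plan says.** The response window is stated three times, and new therapy closes it in none of them.

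- Protocol Section 9.4: "OR is defined as a CR or PR per RECIST v1.1 from the start date until disease progression or death due to any cause".
- Protocol Summary, Statistical Analyses, where the window runs from randomization or "first dose (non-randomized cohorts) until disease progression or death due to any cause".
- Appendix 1, Determination of Best Overall Response: "The best overall response is the best response recorded from the start of the treatment/randomization until disease progression/recurrence".

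Section 9.4 makes a patient a non-responder for an unconfirmed response or for inadequate tumor data. It gives no other reason. For PFS, the same section does have a new-therapy rule: data are censored at the last adequate assessment "for patients who start new anti-cancer treatment prior to an event".

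Scans go on after new therapy. The Schedule of Activities requires them "every 8 weeks until disease progression regardless of initiation of subsequent anticancer therapy" (Combination A, footnote 21; Combination F, footnote 23; the same rule stands for B, C and D). Section 6.3 adds: "Patients whose disease has not progressed at the time of treatment discontinuation will enter into disease follow-up (for tumor assessment").

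Section 5.6 says "Concurrent anticancer therapy with agents other than study treatments is not allowed", but this concerns therapy given alongside study treatment. For the period afterwards, Section 5.6.4 says: "There are no prohibited therapies during the Post-Treatment Follow-up Phase".

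**The concern.** Section 6.4 lists several reasons for stopping treatment other than RECIST progression, among them unacceptable toxicity, global deterioration and refusal. A patient who stops for one of these stays in tumor follow-up and may start another therapy. If the tumor then shrinks enough against the original baseline and the response is confirmed at least 4 weeks later, every element of the primary definition is met. The same patient's PFS would be censored before that response was seen. The two endpoints would then describe different treatments in one patient.

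The error runs one way, since the open window can add responders but cannot remove any. No arm without a study combination is available to offset it. In Cohorts A1 to A5 the conclusion on clinically meaningful activity rests on a responder count; in the other cohorts the ORR estimate and its 90% interval are affected. TTR and duration of response are defined on the same responders and inherit the problem.

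**Working it through.** **Inputs from the protocol (Sections 9.3.1.1 to 9.3.1.3).** Cohorts A1 to A3, each, and A4: 28 patients, null ORR 15%, alternative 35%, reject at 8 or more responders. Cohort A5: 35 patients, null 20%, alternative 40%, reject at 12 or more. All tests are one-sided at 0.05 with power of at least 80%, using the binomial distribution.

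**Step 1: reproduce the stated design.** With X the number of responders:

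- P(X ≥ 8 | 28, 0.15) = 0.0486; P(X ≥ 8 | 28, 0.35) = 0.818.
- P(X ≥ 12 | 35, 0.20) = 0.0344; P(X ≥ 12 | 35, 0.40) = 0.805.

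Both rules meet the stated level and power. No sample-size figure is wrong.

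**Step 2: the weight of one credited response.** It adds 1/28 = 3.6 points of ORR, 1/35 = 2.9 points, 1/25 = 4.0 points or 1/20 = 5.0 points, by cohort size. It turns 7/28 (25.0%, not rejected) into 8/28 (28.6%, rejected), and 11/35 into 12/35. This shows how sensitive the rule is; it does not measure the bias.

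**Step 3: effect on the error rate, by assumption.** Let f be the share of patients not responding to the combination who start a new systemic therapy before RECIST progression, and q the chance that such a patient then has a confirmed CR or PR. The documents give neither. Only non-responders can gain a response, so the null rate p0 becomes

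p0′ = p0 + (1 − p0) × f × q.

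Example: p0 = 0.15, f = 0.10, q = 0.20 gives 0.15 + 0.85 × 0.02 = 0.167, and P(X ≥ 8 | 28, 0.167) = 0.082.

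| f | q | p0′ (28 pts) | error, ≥ 8 of 28 | p0′ (35 pts) | error, ≥ 12 of 35 |
|---|---|---|---|---|---|
| 0 | – | 0.150 | 0.049 | 0.200 | 0.034 |
| 2% | 20% | 0.153 | 0.054 | 0.203 | 0.038 |
| 3% | 30% | 0.158 | 0.062 | 0.207 | 0.044 |
| 5% | 20% | 0.159 | 0.064 | 0.208 | 0.045 |
| 5% | 30% | 0.163 | 0.073 | 0.212 | 0.051 |
| 10% | 20% | 0.167 | 0.082 | 0.216 | 0.058 |
| 10% | 30% | 0.176 | 0.104 | 0.224 | 0.074 |

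Over this range ORR under the null rises by 0.3 to 2.6 points with 28 patients (0.85 × 0.004 to 0.85 × 0.03) and by 0.3 to 2.4 points with 35 (0.80 × 0.004 to 0.80 × 0.03).

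**Step 4: with the window closed at new therapy.** f × q drops out, p0′ = p0, and the error rates return to 0.0486 and 0.0344 with sample sizes and thresholds unchanged.

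**The case against.** The strongest reply is that silence is being read as a rule. No sentence says that responses after new therapy are counted; cut-off rules of this kind often stand in the SAP, to which Section 9 assigns the detailed methodology. Continued scanning does not prove the scans are credited, since PFS ignores those same scans. This stands in part: a reader should not infer that the protocol sets out to count such responses. But the protocol does not leave the window open for later definition. It names the closing events in Section 9.4 and the Protocol Summary, leaves new therapy out, and includes it for PFS in the same section. Applied as written, the definition counts these patients. An SAP rule could repair this, but the protocol text would still say something else, and Section 9 requires an amendment for major changes to the primary endpoint.

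Second, the affected group is narrow. Appendix 1 already makes lesion status not evaluable, absent progression, if a lesion was excised or irradiated and has not reappeared or increased. What remains is mainly new systemic therapy before RECIST progression, then a confirmed response against the original baseline. Discontinuations for treatment-related adverse events reported in Section 1.2 were few: 1 of 86 on utomilumab alone, 2 of 81 on PF-04518600 alone, 1 of 82 on the two together. These come from other studies and leave out refusal and clinical deterioration, so they do not bound f, but they make its low end plausible. At f = 2 to 3%, A5 stays below 0.05. This stands, and it limits the size.

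Third, the scope is smaller than every Phase 2 cohort. No Phase 2 is planned for Combinations C and D, and the Combination B melanoma cohort is not to be opened. Cohorts A6 to A10, B and F have estimates but no hypothesis test. This stands too.

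**Conclusion.** The point holds as a flaw in the endpoint definition. Following the stated window would credit a confirmed response on another systemic therapy to the study combination, and the error can only raise ORR. It affects the ORR estimates in the cohorts analysed and the pass/fail rule in A1 to A5.

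The size is unknown and probably small. The ranges of 0.054–0.104 (28 patients) and 0.038–0.074 (35 patients) rest on assumed values of f from 2 to 10% and q from 20 to 30%, with only non-responders able to gain. They illustrate the possible effect and are not estimates for this trial.

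A reader might infer that the error rate is in fact badly inflated, or that the sample sizes are wrong. The documents support neither: they give no value for f or q, and the stated level and power reproduce. This is a should-fix correction to the definition.

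**What to change.** In Section 9.4, the Protocol Summary and Appendix 1, define objective response and best overall response as a confirmed CR or PR from the start date until progression, death or start of new anticancer therapy, whichever comes first. Require both the initial and the confirming scan to precede the new therapy. TTR then follows without further change. Censor duration of response at new anticancer therapy, in line with PFS.

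The cost is about one sentence in each place, carried into the SAP. Subsequent anticancer therapy is already recorded (Schedule of Activities, Combination A footnote 24, Combination F footnote 26), and the PFS rule already needs its start. No new patients or assessments are required, so the change is still possible for cohorts whose enrollment is complete. ORR may be slightly lower.
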